Blinding and randomization. Neither the research team nor the participants can be blinded to the mode of exercise. However, samples will be labeled in a manner that ensures the individual analyzing the samples will be blinded to the test condition. The order of the testing condition will be randomized and counterbalanced. Once a participant has been verified to meet enrollment criteria and initial sign-off by the study physician and the primary investigator has occurred, participant details (sex, ID number) will be entered into REDCap, which houses the randomization scheme (developed by the GRECC biostatistician). The randomization scheme will include allocation by sex, but not by race/ethnicity or age due to the small sample size.

Submaximal exercise sessions. Each participant will complete 2 exercise sessions that vary by mode: cycling at 70-80% HRmax and treadmill at 70-80% HRmax. HRmax will come from the GXT at screening. Each session will be 60 minutes in duration (plus a 5-minute warm-up at ~50% of HR max) and sessions will be at least 1 week apart. Sources of variance in the CTX response to exercise (primary outcome) other than mode of exercise may include pre-exercise Ca ingestion and the time of day the test is performed, because CTX has a diurnal rhythm.³⁵ To minimize variance from these sources, all exercise tests will be performed in the morning after a calcium-controlled meal and participants will be asked to avoid taking Ca supplements and multi-vitamins for 24 h before a test. Participants will be fasted when they return for the 24-hour blood draw.

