All adverse events (AE's) occurring during the study will be collected, documented, and reported to the PI. Every month the investigators will review AE forms for the month. The study investigators will follow all AE's to the point of a satisfactory resolution. All AEs will be reported to the VA and COMIRB in accordance with institutional policies. Serious adverse events (SAEs), whether or not related to the study protocol, will be reported (within 24 hours) to the local IRB. Any recommended changes to the protocol as a result of monthly monitor meetings will be submitted and approved by the IRB prior to implementation. A summary of the SAEs that occurred during the previous year will be included in the annual progress report. The

principal investigator will be responsible for safety monitoring and review de-identified data on a quarterly basis and as necessary.

E. Potential Scientific Problems:

Recruitment may be a challenge due to the limited number of older women Veterans and the physical activity requirements of potential participants. However, the PI is involved with a clinical exercise program that includes women Veterans in the appropriate age range, and they will be provided the option to volunteer for the proposed research. Additionally, our research group has performed targeted recruiting through our local Community-Based Outpatient Clinics (CBOCs), the Corporate Data Warehouse (CDW), and VA Information and Computing Infrastructure (VINCI) and we have been successful in recruiting similar participants for other VA research studies.

F. Data Analysis Plan:

Sample size and statistical analysis plan. The primary outcome is the change in CTX from pre-exercise to the end of exercise. The change in CTX is hypothesized to be positive for both conditions. With 30 subjects, we will have at least 80% power to detect a change of 0.12 ng/mL or greater between conditions. The study is not powered to detect subgroup differences on the effects of sex. However, exploratory analyses will be conducted to be able to power future studies and to generate hypotheses. To achieve 15 completers per sex, 18 men and 18 women will be enrolled based on an expected drop-out rate of ~20%.

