The effects of treadmill versus cycling exercise on the change in CTX will be evaluated using linear contrasts in a repeated measures maximum likelihood model with all available data. We have utilized this approach in similar experiments,^{9,37,38} and it is conceptually identical to repeated measures analysis of variance but avoids the deletion of cases with missing assessments. Estimates are unbiased under the assumption that missing data are missing at random. Linear contrasts will be used to estimate within-condition changes and between-condition differences in changes over the 60-minute exercise bouts and the recovery periods separately. Primary comparisons will include up to the 24-hour blood draw. Secondary analyses will be conducted utilizing the 48-hour timepoint, but results will be interpreted with caution due to the potential for low sample size. This analysis will be repeated for secondary outcomes (change in iCa, tCa, PTH). The distributions of the outcome measures will be checked. If there are severe departures from a normal distribution, transformations (e.g., natural logarithm) will be applied as appropriate to achieve an endpoint that is approximately normally distributed. To minimize missing data, all participants will be informed of the importance of complete follow-up and encouraged to complete the study per the protocol. Although statistical methods can be used to adjust for missing data, these methods rely on the untestable assumption that data are either **1)** missing completely at random, for which no adjustment is needed, or **2)** missing at random, for which the effect of the “missingness” can be removed through statistical modeling. We will instead focus on preventing missed exercise tests and samples. Due to the mechanistic nature of the studies and the use of the results to guide decisions about a future randomized controlled trial, no adjustments for multiple comparisons will be performed. All analyses will be conducted using SAS software version 9.4 M4 (SAS Institute Inc, Cary, NC, USA) and a p-value ≤ 0.05 defining statistical significance. For the exploratory analyses in SA2, we will use the same statistical approach as SA1 while including sex in the maximum likelihood model. Results will be interpreted with caution due to the low sample size, and will be used to generate hypotheses for future research.

G. Summarize Knowledge to be Gained:

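### The primary CTX contrast between exercise modes has no stated period × time term, although session order is randomised

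*Combined protocol and SAP*

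**What the plan says.** Under Blinding and randomization, Section IV.C states: "The order of the testing condition will be randomized and counterbalanced". It adds that "The randomization scheme will include allocation by sex" and that participant details are "entered into REDCap, which houses the randomization scheme". It does not say that the order actually received will be kept as an analysis variable.

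Section IV.F says the mode effect on CTX change will be "evaluated using linear contrasts in a repeated measures maximum likelihood model with all available data", with contrasts for "between-condition differences in changes over the 60-minute exercise bouts" and, separately, for recovery. It says of the approach that "it is conceptually identical to repeated measures analysis of variance". The only extra term it names is for SA2: "we will use the same statistical approach as SA1 while including sex in the maximum likelihood model". No section names a period, sequence or period × time term, and none says that order will be ignored. The point is therefore left open rather than decided.

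On numbers, Section IV.F states: "To achieve 15 completers per sex, 18 men and 18 women will be enrolled". It claims at least 80% power for a between-mode difference of 0.12 ng/mL with 30 subjects.

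**The concern.** Each person is measured in two sessions. Anything that makes the second session's CTX change differ from the first enters the within-person mode difference with a sign set by order. Counterbalancing cancels this from the mean only if equal numbers complete each order. Even then, the effect stays in the residual unless the model contains it.

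Equal numbers are not assured. Fifteen completers per sex is an odd number, so each sex splits 8/7 at best. If both sexes lean the same way, the overall contrast is 16/14. If they lean opposite ways, the overall contrast is even but the SA2 sex comparison is not.

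At stake are some power for the primary contrast, a small shift whose direction depends on which order loses more people, and the freedom to choose between adjusted and unadjusted results after seeing the data.

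**Working it through.** **Inputs.** From Section IV.F: 30 completers, difference 0.12 ng/mL, power at least 80%, significance at 0.05. Assumed: two-sided test (sidedness is not stated), complete pairs, and power of exactly 80%. The period effect π (session 2 minus session 1 in CTX change) is not in the documents, so values of 0.02 to 0.10 ng/mL are illustrative.

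**The plan's own figure.** No SD is given, so 80% cannot be reproduced independently. Solving the paired t-test (noncentral t, 29 df) for 80% gives a standardised difference of 0.529. Then SD = 0.12/0.529 = 0.227 ng/mL and SE = 0.227/√30 = 0.0414.

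**Model.** For person i, the cycling-minus-treadmill difference in CTX change is D = δ + sπ + e, with s = +1 if cycling comes second and −1 if first. Let a and b be the numbers completing each order, with a + b = 30.

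- Without the term, the estimate shifts by π(a − b)/30. Its estimated squared SE rises by about π²[1 − ((a − b)/30)²]/29.
- With the term, SE = (SD/2)√(1/a + 1/b) on 28 df, with no shift.

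**Cost of the term when π = 0** (80.0% without it), and the shift if it is omitted:

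| Split | Power with term | Loss (points) | SE increase | Shift if omitted |
|---|---|---|---|---|
| 15/15 | 79.9% | 0.10 | 0% | 0 |
| 16/14 | 79.7% | 0.27 | 0.2% | 0.067π |
| 17/13 | 79.2% | 0.81 | 0.9% | 0.133π |
| 18/12 | 78.3% | 1.72 | 2.1% | 0.2π |

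If true power is 90% (SD 0.196), the losses are 0.07 points at 15/15 and 1.27 at 18/12.

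**Effect of omission at 15/15** (simulation). For π = 0.03, 0.06 and 0.10, power is 79.5, 78.0 and 74.2%, against 79.9% with the term. False-positive rates are 4.8, 4.3 and 3.2%, so the test is conservative.

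**Effect of omission at uneven splits, π = 0.06.** The shift is 0.067 × 0.06 = 0.004 ng/mL at 16/14, which is 3% of 0.12 and 0.1 SE. At 17/13 it is 0.133 × 0.06 = 0.008. Power is 75.1% or 80.6% at 16/14, depending on which order is larger (79.7% with the term), and 72.0% or 83.1% at 17/13 (79.2% with the term). If people who leave after session 1 stay in the model, the shifts fall to 0.043–0.057π and 0.086–0.113π, for assumed within-person correlations of 0.3–0.7.

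**How often splits are uneven.** Assume 9/9 by order in each sex and three lost at random per sex after randomisation. The chance that 0, 1, 2 or 3 of a sex's losses come from a given order is 84/816, 324/816, 324/816 or 84/816, that is 0.103, 0.397, 0.397 or 0.103. Combining the sexes gives 15/15 in 2(0.103² + 0.397²) = 34%, 16/14 in 48%, 17/13 in 16% and 18/12 in 2%. The SA2 sex difference would shift by 0, 0.133π, 0.267π or 0.4π with the same four probabilities.

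**Power averaged over those splits:**

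| π (ng/mL) | Without term | With term |
|---|---|---|
| 0 | 80.0% | 79.7% |
| 0.02 | 79.8% | 79.7% |
| 0.03 | 79.5% | 79.7% |
| 0.06 | 77.8% | 79.7% |
| 0.10 | 73.9% | 79.7% |

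Break-even lies at 0.02–0.025 ng/mL, and is the same at SD 0.196.

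**Which term.** A period effect equal at every sample cancels when baseline is subtracted, so only one acting on the change matters. In a generalised least squares check over the 11 scheduled samples with π = 0.06 at 60 minutes, the shifts at 16/14, 17/13 and 18/12 were 0.004, 0.008 and 0.012 with no period term. They were the same with a period main effect only, and zero with period × time.

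**The case against.** The harm rests on an effect for which the documents offer no evidence. An assumed 0.06 ng/mL is half the difference the trial is powered to find. The design also works against a period effect: volunteers are accustomed to both modes (Section IV.B), and they are familiarised on both machines. Tests are in the morning after a calcium-controlled meal, and each person's stored samples are assayed in one batch (Section IV.C). Below break-even the term slightly lowers power. Validity is not in danger: the highest false-positive rate found was 5.3%, needing both an 18/12 split and an effect of 0.10. All this stands and makes the gain modest. It does not rule out a period effect, since familiarisation lasts 20 minutes per mode against 60-minute sessions and the gap between sessions has only a minimum.

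The split probabilities depend on a 9/9 start and on loss after randomisation. The protocol gives no block size and does not say whether people who withdraw at familiarisation have already been randomised. If most loss comes earlier, the larger imbalances become rare. That is fair, and 16/14 is the case to keep in mind.

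The cost was worked out for complete pairs, not for missing samples. If maximum likelihood is meant literally, with variance divided by n, the paired analogue's false-positive rate goes from 5.4% without the term to 5.8% with it. In an illustrative 48-hour subset of 10 split 7/3, the confidence interval widens by 11%. These costs are real but small or secondary, and they do not alter the primary comparison.

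Finally, the plan cites earlier experiments for its method, and those may have included order. The documents do not say so.

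**Conclusion.** The concern holds. The trial randomises session order, but the stated model for its primary contrast has no term for it. This is an under-specification worth correcting, not a flaw that invalidates the analysis.

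Averaged over the assumed splits, including the term changes power by −0.3 points if there is no period effect, +1.9 (79.7 − 77.8) at 0.06 ng/mL and +5.8 (79.7 − 73.9) at 0.10. It also removes a shift of 0.004 ng/mL at 16/14 when the effect is 0.06. If loss is unrelated to order, the direction of that shift is random.

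These figures assume an additive period effect of unknown size, a two-sided 0.05 test, 80% base power and 30 complete pairs. The averages also assume a 9/9 start in each sex.

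**What to change.** In Section IV.F, list the fixed effects for SA1 as mode, time, mode × time, period and period × time. For SA2, list the same plus the planned sex terms. Define period by the session order actually received, and record it as an analysis variable. State that this removes an additive period effect only, not carry-over or a mode-by-period interaction. Saying whether estimation is by full or restricted maximum likelihood would also settle the small-sample question raised above.

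The change needs SAP wording, one line in the SAS model and one recorded variable, with no new data. Period and period × time add 11 parameters over the 11 scheduled samples. With complete samples, the 60-minute contrast matches a paired regression on order, so it loses one degree of freedom (29 to 28) and takes the SE increases tabulated above. The cost with missing samples has not been computed and should be checked when the model is finalised.

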Blood collections (Fig 4) and assays. For each of the exercise tests, two pre-exercise blood samples will be obtained as described in the preceding paragraph. Blood samples (10 mL each) will be obtained after 15, 30, 45, and 60 minutes (exercise), and at 75, 90, 120, and 300 minutes during recovery, and 24 hours after the end of exercise. An additional blood sample 48 hours after exercise will be available as an optional procedure for analysis of iCa, P1NP, and CTX. After exercise, participants will remain in a semi-recumbent position for the duration of recovery. Blood samples will be processed by the CTRC Core Laboratory (partial off-site waiver will be pursued) and stored at -80°C. Samples from all exercise sessions for an individual will be analyzed in batch to minimize batch effects. The exceptions to this will be the parameters measured in real time (hematocrit (**HCT**), iCa, pH) during the study visits by the iSTAT analyzer (Abbot Point of Care, Princeton, NJ). Serum (or plasma) assays will include: **1)** PTH by immulite two-site enzyme immunoassay (Siemens, Erlangen, Germany; CTRC Core Lab), **2)** CTX by chemiluminescence (Immunodiagnostic Systems, Boldon Business Park, UK; CTRC Core Lab), **3)** P1NP by chemiluminescence (Immunodiagnostic Systems; CTRC Core Lab), and **4)** tCa by indirect ion-selective electrode (Beckman Coulter Inc; UCH Clinical Lab). Laboratories where assays will be conducted are CAP and CLIA certified. Laboratory-specific intra- and inter-assay coefficients of variations are generally lower than those determined by the manufacturers. PTH, CTX, iCa, and tCa, concentrations during and after exercise will be adjusted for shifts in plasma volume as previously described.⁸ These outcomes cannot be assayed in a VA laboratory due to the lack of the necessary combined analysis system. Performing each assay individually in a wet lab would double the blood required, increasing participant burden and risk.

Feasibility measures. Participants will be asked to rate multiple aspects of their experience, including preference for each mode of exercise, ease of getting to and from the exercise facility, and their likelihood of participating in a center-based exercise program that would require multiple trips to the VA facility several times per week over multiple months. This information will be used to inform future intervention designs.

[figure not shown]

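### The primary CTX contrast fixes the slope on the between-session baseline difference at 1; this is unbiased, but it may lose precision that a prespecified baseline adjustment would recover at little cost.

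*Combined protocol and SAP*

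**What the plan says.** Section IV.F defines the endpoint: "The primary outcome is the change in CTX from pre-exercise to the end of exercise". The mode effect comes from a repeated measures maximum likelihood model: "Linear contrasts will be used to estimate within-condition changes and between-condition differences in changes over the 60-minute exercise bouts". Sex, for the exploratory second aim, is the only further model term named. The plan mentions neither a pre-exercise covariate nor a constraint that pre-exercise means be equal across modes.

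On power the section says: "With 30 subjects, we will have at least 80% power to detect a change of 0.12 ng/mL or greater between conditions". The threshold is "a p-value ≤ 0.05 defining statistical significance". No SD, correlation or sidedness is given.

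On design, section IV.C says "The order of the testing condition will be randomized and counterbalanced" and "sessions will be at least 1 week apart". For each session, "two pre-exercise blood samples will be obtained as described in the preceding paragraph": one semi-recumbent, the other on or at the equipment, seated or standing, just before exercise starts. The plan does not say which of the two is the baseline.

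**The concern.** The plan does not write the model out. If it has a separate mean for each mode and time, which is the usual form, then with complete data the contrast equals the raw difference in mean changes. Having the pre-exercise value in the model as a response recovers no precision by itself.

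Order is randomised, so a person's difference in resting pre-exercise CTX between the two sessions should be zero in expectation; what is seen is chance. Subtracting all of it is the most efficient choice only if the 60-minute difference carries that chance difference forward one for one. Otherwise an estimated slope targets the same mode effect with a smaller variance. At stake is power on the one comparison for which the trial states any, with 30 completers and a recruitment challenge that section IV.E acknowledges.

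**Working it through.** **Inputs from the documents.** n = 30; difference 0.12 ng/mL; power at least 80%; alpha 0.05 (taken as two-sided). Not given, so assumed over a range: rho and k, defined below.

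**Step 1: the plan's own figure.** Without an SD the 80% cannot be checked forwards, so I solved backwards. For a paired t-test with 29 df, critical value 2.045, 80% power needs a noncentrality of about 2.90. The implied SD of the paired difference in changes is 0.12 × √30 / 2.90 = 0.227 ng/mL, a standardised effect of 0.12 / 0.227 = 0.53. Everything below starts from exactly 80% at this SD.

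**Step 2: variance ratio.** For each person take cycling minus treadmill. Let X be that difference in pre-exercise CTX and Y that difference at 60 minutes. Let rho = corr(X, Y) and k = SD(Y)/SD(X). In units of SD(X) squared:

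- change contrast, Y − X: variance k² + 1 − 2·rho·k
- adjusted, Y given X: variance k²(1 − rho²)
- best slope: rho × k
- ratio R = k²(1 − rho²) / (k² + 1 − 2·rho·k), which is (1 + rho)/2 when k = 1

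R equals 1 exactly when rho × k = 1 and is below 1 otherwise. Estimating the slope multiplies R by about 1 + 1/(n − 3) = 1 + 1/27 = 1.037 and leaves 28 df.

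Example, k = 1 and rho = 0.5: R = 0.75; 0.75 × 1.037 = 0.778; power 88.7%.

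**Step 3: power after adjustment, slope cost included.**

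| k | rho | slope | R × 1.037 | power |
|---|---|---|---|---|
| 1 | 0.5 | 0.50 | 0.778 | 88.7% |
| 1 | 0.7 | 0.70 | 0.881 | 84.6% |
| 1 | 0.8 | 0.80 | 0.933 | 82.5% |
| 1 | 0.9 | 0.90 | 0.985 | 80.5% |
| 1 | 0.95 | 0.95 | 1.011 | 79.5% |
| 1.25 | 0.5 | 0.63 | 0.926 | 82.8% |
| 1.25 | 0.6 | 0.75 | 0.976 | 80.8% |
| 1.25 | 0.7 | 0.88 | 1.017 | 79.2% |
| 1.25 | 0.8 | 1.00 | 1.037 | 78.5% |
| 1.5 | 0.5 | 0.75 | 1.000 | 79.9% |
| 1.5 | 0.6 | 0.90 | 1.030 | 78.7% |
| 1.5 | 0.7 | 1.05 | 1.035 | 78.5% |
| 1.5 | 0.8 | 1.20 | 0.988 | 80.4% |

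The worst case is slope = 1, where R = 1 and only the slope cost remains: 80% falls to 78.5%.

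**Step 4: simulation** (20,000 trials per setting, k = 1), change contrast against adjusted: rho 0.5, 79.9% against 88.6%; rho 0.7, 79.9% against 84.8%; rho 0.9, 80.3% against 80.6%; rho 0.95, 80.0% against 79.6%. Both estimators centred on 0.12, so neither is biased.

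**Step 5: what each rho implies.** With k = 1, SD(X) = 0.227/√(2 − 2·rho), and the within-person session-to-session SD of pre-exercise CTX is that divided by √2. At rho 0.5 this is 0.227/√2 = 0.16 ng/mL. At rho 0.9 it is 0.507/√2 = 0.36 ng/mL, three times the target difference, although section IV.C standardises time of day, meal and supplements to reduce such variation. This leans towards a moderate rho if k is near 1. It does not establish one.

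**The case against.** The strongest reply is that neither the size nor the sign of the benefit is known. The plan expects CTX to rise in both conditions; if people vary in that rise from session to session, k above 1 is plausible. Over k of 1.25 to 1.5 and rho of 0.5 to 0.8, adjustment moves power only between −1.5 and +2.8 points. The change contrast is conventional, matches hypothesis H1a's wording about a greater increase, and suits a pilot. All of that stands, and it is why the point is put conditionally.

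Four stronger readings are tempting, and the documents support none of them.

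- That the planned contrast is biased or inflates type I error. Randomised order rules this reading out.
- That it certainly wastes precision. That needs rho and k, which are not given.
- That subtracting the baseline over-corrects whenever rho is below 1. The condition is rho × k below 1. At k = 1.25 and rho = 0.8 the contrast is already optimal; at k = 1.5 and rho = 0.8 it under-corrects.
- That the same loss applies to PTH, iCa, tCa and P1NP. Nothing was computed for them and no inputs exist; the plan's list of outcomes for repeating this analysis also omits P1NP.

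A fair practical objection is that a constrained longitudinal model is more than a one-line change. With 11 scheduled samples per session, 22 per person, an unstructured covariance has 22 × 23 / 2 = 253 parameters, too many for 30 people. Any simpler structure determines the implied slope, so it must be stated in advance. The two-variable regression avoids this.

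**Conclusion.** The point holds as a worthwhile improvement, not as an error. The primary contrast is valid, but it fixes at 1 a slope that could be estimated from data already collected. With equal SDs, the gain is about 9 power points at rho 0.5, 5 at 0.7, 2.5 at 0.8 and almost none at 0.9. With an SD ratio of 1.25 to 1.5 and rho 0.5 to 0.8, power ends between about 78.5% and 82.8%. The loss is capped at about 1.5 points. The possible gain is larger than the possible loss, which is the case for adjusting.

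This rests on a two-sided 5% test, exactly 80% power for the change contrast (implied SD 0.227 ng/mL), 30 complete pairs, a resting baseline whose expected value is the same before either mode (so no mode-dependent carry-over across the gap of at least a week), and assumed values of rho and k. No gain is claimed for the secondary markers.

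**What to change.** In section IV.F, before analysis:

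1. Name the semi-recumbent pre-exercise sample as the baseline. The second sample is taken seated or standing at the equipment, so it may already differ by mode through posture. This is worth settling whatever rho is.
2. For the primary CTX contrast at 60 minutes, regress each person's cycling-minus-treadmill difference on the same person's difference in that baseline, left uncentred, and test the intercept. Centring it would turn the intercept back into the unadjusted difference at 60 minutes. Alternatively, use a repeated measures model with pre-exercise means constrained equal across modes and a covariance structure stated in advance.
3. Keep the raw difference in changes as a sensitivity analysis.
4. State the SD behind the power figure and, if the group's earlier data allow, the values of rho and k. If the expected slope is close to 1, there is little reason to change the primary contrast.

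The same approach can be used for the secondary markers, without promising a gain. Cost: a few sentences of text, one degree of freedom, a possible loss of about 1.5 power points, and no new samples or participants.

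### Does describing CTX comparisons up to 24 hours as primary leave the trial without a single defined primary test?

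*Combined protocol and SAP*

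**What the plan says.** Section IV.F opens by fixing the outcome: "The primary outcome is the change in CTX from pre-exercise to the end of exercise". Two sentences later comes the sample-size claim: "With 30 subjects, we will have at least 80% power to detect a change of 0.12 ng/mL or greater between conditions".

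The model description follows. Linear contrasts are to estimate "between-condition differences in changes over the 60-minute exercise bouts and the recovery periods separately". Then comes the sentence at issue, "Primary comparisons will include up to the 24-hour blood draw", and directly after it "Secondary analyses will be conducted utilizing the 48-hour timepoint", with a caution about small numbers. The analysis is then repeated for the secondary outcomes. Because the study is mechanistic and feeds a later trial, "no adjustments for multiple comparisons will be performed".

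Section IV.C (blood collections and assays) schedules post-exercise samples "at 75, 90, 120, and 300 minutes during recovery, and 24 hours after the end of exercise". It describes the last draw differently: "An additional blood sample 48 hours after exercise will be available as an optional procedure".

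In Section I, SA1 marks CTX as primary without a time point. H1a predicts more resorption with cycling and also names no time point. H1b, on P1NP, is tied to 24 hours.

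**The concern.** The word primary is attached first to one CTX change, ending when exercise ends, and then to a plural set of comparisons reaching 24 hours. Within that set nothing is ranked; only the 48-hour analysis is put lower. Since H1a has no time point, a literal reader could let either the exercise or the recovery contrast decide it.

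Two things would then be at stake. With no multiplicity adjustment, the 5% error rate for the primary question holds only if one contrast answers it. And the plan would have no rule for the case where the exercise and recovery contrasts disagree.

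**Working it through.** **1. The plan's own figure.** Inputs from Section IV.F: n = 30 (each person does both modes), difference 0.12 ng/mL, power at least 80%, significance level 0.05. Two-sided testing is an assumption, because the section gives only the p-value threshold. No SD is stated, so the power cannot be reproduced; the SD of the within-person difference that it implies can be.

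- Normal approximation: SD = 0.12 × √30 / (1.960 + 0.842) = 0.657 / 2.802 = 0.235 ng/mL.
- With the t distribution on 29 degrees of freedom: 0.227 ng/mL.

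The claim concerns one detectable difference and comes two sentences after the single primary outcome. It fits one test of that outcome.

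**2. The statements side by side.**

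- *Primary outcome:* singular, with a marker (CTX) and a window (before exercise to its end).
- *Contrasts:* exercise and recovery estimated separately. The exercise-period contrast is the primary outcome compared between modes, so no further choice among contrasts is needed to find it.
- *Primary comparisons up to 24 hours:* followed at once by a separate, secondary analysis of the 48-hour draw, which Section IV.C makes optional. The pair reads as a boundary on the data: samples every participant is scheduled to give, against a sample only some will give.
- *Why 24 hours:* it is the last mandatory draw. H1b also needs it, although this is only a supporting inference, since the list of secondary outcomes in Section IV.F omits P1NP and the sentence follows text on CTX.

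Read this way, the statements do not conflict.

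**3. What the looser reading would cost.** Suppose either the exercise or the recovery contrast could be claimed as primary. Simulation: 400,000 trials per correlation, no true mode difference, 30 paired differences, each contrast tested at |t| > t(0.975, 29). The documents give no correlation between the contrasts, so a range is assumed.

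| Assumed correlation | False difference, either direction | False difference in H1a's direction |
|---|---|---|
| 0.9 | 7.1% | 3.6% |
| 0.7 | 8.5% | 4.2% |
| 0.5 | 9.1% | 4.6% |
| 0.3 | 9.5% | 4.7% |
| 0 | 9.7% | 5.0% |
| One contrast only | 5.0% | 2.5% |

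Check at independence: 1 − 0.95² = 9.75% and 1 − 0.975² = 4.94%.

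If recovery change were measured from the end of exercise, the correlation could be negative. At −0.3, −0.5 and −0.7 the either-direction rates are 9.5%, 9.1% and 8.4%, inside the same range. If H1a were instead tested one-sided at 0.05, one contrast would give 5% and two about 6.8% to 10.0% (correlations from 0.9 to −0.5).

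A third, separate 24-hour contrast is not carried forward. Section IV.F names two periods. Counting 24 hours apart from recovery would rest only on how Section IV.C lists the samples and on the 4-hour recovery in the Figure 4 caption.

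**4. Adjustment as an alternative.** At the implied SD of 0.227, a Bonferroni split over two contrasts would lower power per contrast from 80% to 70.2%. That is a real price for guarding against a reading the plan does not require.

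**The case for a change.** The strongest case for a change runs as follows. The word comparisons is plural, and one reaching 24 hours cannot be the end-of-exercise change. The authors gave H1b a time point and H1a none. Section II reports that resorption stays raised for at least 4 hours after exercise, so a recovery contrast is a credible test of H1a, not a contrived one. Declining adjustment does not say which test is primary; without adjustment, naming one test in advance is all that holds the error rate. The results will guide a later randomised trial, and a clarification costs almost nothing.

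Much of this stands. The sentence is loosely worded, and an explicit ranking would read better. What does not stand is that the naming has been left undone: the opening sentence of Section IV.F does it. An author who presented a recovery contrast as the primary result would contradict that sentence, and any reader of the plan could see it. A rule for contrasts that disagree is not needed when one outcome is primary; the recovery result is then reported beside it, unadjusted, as the plan openly says.

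One neighbouring matter is separate. Section IV.C takes two pre-exercise samples, and Section IV.F does not say which is the baseline. That has no bearing on the sentence discussed here or on the error rates above.

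**Conclusion.** The wording is ambiguous, but the plan is not contradictory and no change is called for. The single powered outcome already identifies the deciding contrast, and the sentence about 24 hours most naturally separates the main samples from the optional 48-hour draw. Analysts following Section IV.F would fit the same model, report the same end-of-exercise contrast at 0.05 and disclose the lack of adjustment, with or without an added ranking line.

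The rise from 5% to about 7% to 10% applies only if a recovery contrast is also treated as primary, against the stated outcome. It further rests on assumed two-sided tests and assumed correlations from 0.9 to 0. The conclusion depends on reading the 24-hour sentence as a data window; if the investigators did intend several primary CTX contrasts, those rates would apply and the plan would need a decision rule. Nothing in the documents points clearly to that intention.
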